### **Secondary Outcomes Analysis**

Study Protocol. Version August 9, 2024

Full Study Title: Interruption versus Non-Interruption Reminders for Statin tHerApy in Primary Care (INIRSHA-PC). A Randomized Trial.

Primary Investigator: [name], MS

The secondary outcomes include a binary outcome of statin prescription within 12 months post-randomization and first post-randomization LDL-C level. To compare each outcome between the interruptive reminder arm, non-interruptive reminder arm, and control arm, a logistic regression will be used to analyze the binary outcome of statin prescription within 12 months post-randomization while a linear regression analysis will be performed to compare LDL-C level between the arms. If the distribution of LDL-C levels is highly skewed, an ordinal logistic regression analysis will be used in place of a linear regression. The analysis set for the secondary outcomes will be described in the SAP.

### **Exploratory Outcomes Analysis**

A logistic regression will be performed to compare the binary outcomes between intervention arms. Time from enrollment BPA firing to statin prescription will be compared between intervention arms using a Cox proportional hazard model and the differences in the outcome between arms will be visualized using a Kaplan-Meier curve.

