## 7.6 Duration of the Intervention

As the randomization is anchored to the provider's patient, the provider will receive the same educational intervention for a given patient throughout the course of the study. For interruptive and non-interruptive alert arms, clinicians may or may not still be eligible for a repeat alert depending on how they interacted with the initial alert. If the patient is on a statin, the clinician will not be shown a repeat alert. If the clinician did not prescribe a statin and chose an acknowledgement reason such as "statin is contraindicated", the alert will not be shown again. If the clinician simply closed or "canceled" the alert during the first visit, or if the clinician did not interact with a non-interruptive alert, the alert will be displayed again at the next visit.

Study Protocol. Version August 9, 2024

Full Study Title: Interruption versus Non-Interruption Reminders for Statin tHerApy in Primary Care (INIRSHA-PC). A Randomized Trial.

Primary Investigator: [name], MS

Any alert shown will be customized according to the patient's current clinical characteristics. For example, if the dose intensity indicated for the patient has changed, the reminder will display the currently recommended dose intensity.

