### **Justification for the Primary Effectiveness Outcome**

The primary purpose of the reminder is to encourage statin prescription. Most prescribing as a result of the reminder is likely to occur within the first 24 hours after the alert.

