## 12.0 Statistical Considerations

### **Study Design and Sample Size Consideration**

If we assume that the statin prescribing rate for the control arm (i.e., routine care, or “silent” alert) is 3%, an estimate derived from current clinical data, and the statin prescribing rate for the interruptive statin reminder arm is 6%, a total of 3,006 patients (1,002 patients per arm) would provide 90% power to detect the difference in the statin prescribing rates between the two arms at a type I error rate of 0.05. With a conventional study design, our planned sample size could be a total of 3,000 patients (1,000 patients per arm).

However, considering that this study is a 3-arm trial with substantial uncertainty on the effect size for both the interruptive statin reminder arm and the non-interruptive statin reminder arm, we designed an adaptive clinical trial with sample size adaptation. When sample size reaches 2,250 patients (750 patients per arm), we will conduct an interim analysis to re-estimate the sample size. At the interim, we will calculate the conditional power and re-estimate the sample size that will provide sufficient power. Should the interim analysis confirm that the originally

Study Protocol. Version August 9, 2024

Full Study Title: Interruptive versus Non-Interruptive Reminders for Statin Therapy in Primary Care (INIRSHA-PC). A Randomized Trial.

Primary Investigator: [name], MS

planned sample size of 3,000 patients (1,000 patients per arm) is sufficient, we will proceed without further adjustment and stop recruiting patients when the sample size reaches 3,000 patients (1,000 patients per arm) or the stopping decision is made, whichever occurs later. However, if the interim analysis indicates the need for an increased sample size, we will adjust accordingly based on the re-estimated sample size with the constraint of the maximum sample size of a total of 6,000 patients (2,000 patients per arm).

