Based on baseline rates of eligible patient visits, we estimate a possible sample size of 3,931 over a course of 6 months, and 7,830 over a course of 12 months. If we assume that the statin prescribing rate for the control arm (i.e., no reminder, or routine care) is 3% (an estimate derived from current clinical data) and the statin prescribing rate for the interruptive statin reminder arm is 6% (an estimate based on a clinically meaningful doubling of the current prescribing rate with an active alert), a total of 3,006 patients (1,002 patients per arm) would provide 90% power to detect the difference in the statin prescribing rates between the two arms at a type I error rate of 0.05. With a conventional study design, our planned sample size could be a total of 3,000 patients (1,000 patients per arm).

However, considering that this study is a 3-arm trial with uncertainty on the effect size for both the interruptive statin reminder arm and the non-interruptive statin reminder arm, and potential chance of imbalance across arms, we designed an adaptive clinical trial with sample size adaptation. When the sample size reaches at least 2,250 patients (750 patients per arm), we will conduct an interim analysis to re-estimate the sample size. At the interim, we will calculate the conditional power and allow sample size re-estimation. Should the interim analysis confirm that the originally planned sample size of 3,000 patients (1,000 patients per arm) provides sufficient power, we will proceed without further sample size adjustment and stop recruiting patients when the sample size reaches 3,000 patients (1,000 patients per arm) or the stopping decision is made, whichever occurs later. However, if the interim analysis indicates the need for an increased sample size, we will adjust accordingly based on the re-estimated sample size with the constraint of the maximum sample size of a total of 6,000 patients (2,000 patients per arm).

Interventions

Interruptive reminder arm:

Providers will receive education via a pop-up alert at the time that the chart is opened for eligible patient visits assigned to the interruptive reminder arm.

Non-interruptive reminder arm:

Providers will be able to seek out education at their own initiative via an on-demand reminder within a section of the chart for eligible patient visits assigned to the non-interruptive reminder arm.

No reminder arm (routine care):

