Patient age, sex, Charlson Comorbidity Index, type of patient statin therapy recommended to provider, baseline LDL-C level, ASCVD disease, diabetes, chronic kidney disease, prior statin prescription, visit type (in person or telemedicine), provider role, and time from enrollment to follow-up LDL-C level measurement.

Population-Level Summaries

Odds ratios (ORs) will be used for the analysis of binary (and ordinal) outcomes. For the analysis of the first LDL-C level measured during the follow-up, the estimates of mean differences in LDL-C levels, comparing interruptive reminder vs. no reminder arms, non-interruptive reminder vs. no reminder arms, and interruptive reminder vs. non-interruptive reminder arms will be used if a linear regress model is used. Hazard ratio (HR) will be used for the analysis of time to statin prescription.

Handling Missing Data

We do not expect missingness in our primary outcome and a secondary outcome of statin prescription within 12 months after BPA firing. Some missingness is expected for the first LDL-C level measured during the follow-up. For these missing outcomes, if a prior LDL-C level is available, the outcome will be imputed using the last known LDL-C level prior to the follow-up period; otherwise, the patient will be excluded in this analysis. For the exploratory outcomes, a complete case analysis will be performed without imputing the missing outcomes.

Missing covariates are not expected, or to be small percentage if occurs, which will be imputed using a single imputation. If missing data are substantial, multiple imputation will be used to handle missing covariates.

Intercurrent Events

To handle intercurrent event due to death or switching providers to other institutions, a whilealive strategy will be used.

Differential Treatment Effects

We will explore differential treatment effects for the primary endpoint only. Differential treatment effects will be explored by examining the interaction between the intervention arm

PI: [name], MS

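### Time to statin prescription is summarised by one 12-month Cox hazard ratio, with no split at 24 hours and no summary free of proportional hazards, although most alert-driven prescribing is expected in the first 24 hours

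*Protocol*

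**What the plan says.** Protocol 12.0, Exploratory Outcomes Analysis: "Time from enrollment BPA firing to statin prescription will be compared between intervention arms using a Cox proportional hazard model", with a Kaplan-Meier curve as the display. The SAP repeats this under its analysis of the exploratory endpoints and, under Population-Level Summaries, fixes the effect measure: "Hazard ratio (HR) will be used for the analysis of time to statin prescription". The clock starts at the enrollment firing, and Protocol 8.4 collects the date and time of signing up to 365 days. Neither document plans a proportional-hazards check, a time split, a time-varying effect or a second numerical summary.

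On when the effect should appear, Protocol 8.1 justifies the 24-hour primary outcome as follows: "Most prescribing as a result of the reminder is likely to occur within the first 24 hours after the alert".

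On what happens later, Protocol 7.6 and the SAP's randomization section keep a patient's assignment for later visits. If the alert was cancelled, or a non-interruptive alert was not used, "the alert will be displayed again at the next visit".

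**The concern.** A Cox model with only arm indicators estimates one ratio and treats it as constant over the year. The protocol's own reasoning points to a larger ratio just after firing and a smaller one later. The fitted ratio is then an average of the two, weighted largely by how many prescriptions fall in each period. The number in the later period depends on routine prescribing over the rest of the year, which the plan does not state. The same day-1 effect could therefore be reported as quite different hazard ratios.

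The stated exploratory aim (Protocol 3.0) is the effect on time from firing to prescribing. A single averaged ratio can answer that poorly. In the limiting case where alerts only bring forward prescriptions that would have been written within the year anyway, the ratio is close to 1.

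**Working it through.** **The plan's own figure.** Protocol 12.0 states that "a total of 3,006 patients (1,002 patients per arm) would provide 90% power" for 3% versus 6% "at a type I error rate of 0.05". With the pooled-variance formula, two-sided:

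n = [1.96·√(2·0.045·0.955) + 1.2816·√(0.03·0.97 + 0.06·0.94)]² / 0.03² = (0.5746 + 0.3747)² / 0.0009 = 1,001.4, so 1,002 per arm and 3,006 in total. The figure reproduces. It concerns the 24-hour outcome; the documents give no hazard ratio, event count or power for time to prescription.

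**Hazard ratio in the first 24 hours.** Cumulative hazards are −ln(0.97) = 0.0305 and −ln(0.94) = 0.0619. Their ratio is 2.03.

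**Single 12-month ratio.** Assume equal hazards after 24 hours, with a fraction L of those still unprescribed receiving a statin by day 365. L is assumed, because the documents do not give it. The large-sample Cox ratio θ solves

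Σ [d₁ − (d₀ + d₁)·θS₁/(S₀ + θS₁)] = 0,

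where d and S are the expected events and the proportion still unprescribed in each arm over time. A hand check is the ratio of 12-month cumulative hazards, (0.0619 + Λ)/(0.0305 + Λ), with Λ = −ln(1 − L).

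**Restricted mean time.** The arms differ by 0.03·exp(−λu) at u days after day 1. The difference over 365 days is therefore 0.03 × 364 × L/Λ days; the first day itself adds about 0.015.

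| L (assumed) | 12-month rates | Hand check | Single Cox HR | Events in first 24 h | Restricted mean difference (days) |
|---|---|---|---|---|---|
| 2% | 4.9% v 7.9% | 1.62 | 1.63 | 70% | 10.8 |
| 3% | 5.9% v 8.8% | 1.52 | 1.53 | 61% | 10.8 |
| 5% | 7.9% v 10.7% | 1.38 | 1.40 | 49% | 10.6 |
| 10% | 12.7% v 15.4% | 1.23 | 1.25 | 32% | 10.4 |
| 20% | 22.4% v 24.8% | 1.12 | 1.14 | 19% | 9.8 |
| 30% | 32.1% v 34.2% | 1.08 | 1.10 | 14% | 9.2 |

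Simulated trials of 1,000 per arm gave 1.37, 1.24, 1.13 and 1.10 for L of 5, 10, 20 and 30%. Approximate power of the Cox contrast at 1,000 per arm is 0.61, 0.45 and 0.29 for L of 5, 10 and 20%, against 0.90 for the 24-hour outcome.

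**If repeat alerts work.** Suppose the alert fires again and gives 3% versus 6% at one, two or three later visits (assumed).

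- No prescribing between visits: the single ratio stays at 2.03.
- 10% prescribed between visits: 1.39, 1.49, 1.56.
- 20% prescribed between visits: 1.24, 1.31, 1.38.

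The dependence on background prescribing is weaker but remains.

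**If alerts only bring prescriptions forward.** Suppose both arms reach the same 12-month total. The single ratio is about 1.02 for totals from 10% to 40%. At a total of 10%, the restricted mean difference is 364 × [0.07/ln(0.97/0.90) − 0.04/ln(0.94/0.90)] = 364 × (0.9346 − 0.9199) ≈ 5.4 days. At 40% it is 364 × [0.37/ln(0.97/0.60) − 0.34/ln(0.94/0.60)] ≈ 4.7 days. The restricted mean registers an acceleration that the hazard ratio does not.

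**The case against.** The strongest reply is that little depends on this number. The 24-hour effect is the primary endpoint and the 12-month cumulative effect is a secondary one, each with its own logistic regression and 95% CI. The Kaplan-Meier curves would show early separation. The outcome is one of four exploratory endpoints and drives no sample size or decision rule. Under non-proportional hazards a Cox ratio is still an average comparison, not an invalid one. A 0-24 hour hazard ratio largely re-expresses the primary result, and cumulative incidence at 24 hours and 12 months would repeat the existing endpoints on another scale. All of this stands. It limits the severity and rules out a fix that merely duplicates those analyses.

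Three stronger readings are tempting, and the documents do not support them:

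- **The alert acts only in the first 24 hours.** Protocol 8.1 speaks of most prescribing, and only as likely. Alerts can fire again within the 12 months, so equal later hazards are an assumption.
- **The single ratio mainly reflects background prescribing.** That needs a 12-month background rate, which is not given. In the equal-hazards scenario, later events become the majority only when L exceeds about 4.5 to 5%; at 2 to 3%, 61 to 70% of events fall in the first 24 hours.
- **A strong day-1 effect would be lost from the trial's report.** The primary analysis would report it directly.

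The reply does not cover the timing question itself. Neither logistic analysis measures time gained, the curves carry no numerical contrast, and the one planned number depends on a quantity the plan leaves open.

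**Conclusion.** The point holds as a minor one. The only numerical summary planned for time to prescription assumes a constant ratio that the protocol's own expectation makes unlikely. With 3% versus 6% in the first 24 hours and equal hazards later, 2.03 becomes about 1.63 to 1.10 as later prescribing goes from 2% to 30%. Over the same range the restricted mean difference stays between 10.8 and 9.2 days.

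These sizes rest on the planning rates, an assumed constant later hazard, complete follow-up to day 365 and an assumed range for L. Effective repeat alerts would keep the single ratio higher. The figures are for interruptive reminder versus control and apply to any contrast with the same rates.

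**What to change.** In the SAP's exploratory analysis and Population-Level Summaries:

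1. Make the difference in restricted mean time to prescription over 365 days, with a 95% CI for each arm contrast, the numerical summary beside the planned Kaplan-Meier curves.
2. Report the Cox hazard ratio in two parts, 0-24 hours and after 24 hours. Label the later part descriptive: it is restricted to patients not prescribed on day 1, a group formed after randomization. It would still indicate whether the arms continue to differ, for example through repeat alerts.
3. State how patients never prescribed are censored. The SAP does not say, and both summaries need it.

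The cost is a few lines of SAP text and code, and a few more exploratory numbers per contrast. No new data are needed, because Protocol 8.4 already collects the date and time of signing. The primary and secondary analyses do not change.

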### **Secondary Analysis**

A secondary, covariate-adjusted analysis will be performed for the primary and the secondary outcomes using the same regression analysis methods as listed above. The selected covariates for each outcome will be detailed in the formal SAP.

## **13.0 Privacy/Confidentiality Issues**

At no time during the course of this study, its analysis, or its publication will patient or provider identities be revealed in any manner. The minimum necessary data containing patient or provider identities will be collected. As quickly as feasible, all data collected will be stored on secure, password-protected servers with user-level access control. All patients will be assigned a unique study number for use in the computerized database. At the time of publication all identifiers will be removed.

## **14.0 Follow-up and Record Retention**

Clinician BPA interactions, statin prescription status, and patient LDL-C outcomes will be followed after the intervention for one year. All data will be stored on secure servers with user-level access control until the time of study publication. At the time of publication, a de-identified version of the database will be generated. After study close, the PI will retain study data for a minimum of 3 years, consistent with institutional and federal policies.

## **15.0 Data and Safety Monitoring**

Given the minimal risk of the study intervention, which is a reminder directed at clinicians to recommend an eligible patient receives guideline-based statin prescription, the principal investigator will serve as the Data and Safety Monitor. The PI will regularly monitor data from this trial, review and assess the performance of its operations, and consult with co-investigators and the IRB with respect to:

- Review of adverse events

Study Protocol. Version August 9, 2024

Full Study Title: Interruptive versus Non-Interruptive Reminders for Statin tHeRApy in Primary Care (INIRSHA-PC). A Randomized Trial.

Primary Investigator: [name], MS

- Possible modifications in the clinical trial protocol

Study Protocol. Version August 9, 2024

Full Study Title: Interruption versus Non-Interruption Reminders for Statin tHerApy in Primary Care (INIRSHA-PC). A Randomized Trial.

Primary Investigator: [name], MS


With the widespread use of EHRs and the implementation of reminders, the decision to build an alert as interruptive or non-interruptive is an important one which must balance potential alert fatigue with potential positive effects on adherence to clinical guidelines which improve quality of care for patients. Rigorous studies are needed to gather evidence to help clinical informaticians when making decisions about the design of CDS interventions. Findings from such studies would have implications for the thousands of alerts displayed to clinicians each year. To address this knowledge gap, we will conduct a prospective, randomized trial of reminders delivered to clinicians seeing patients in primary care clinics, comparing interruptive vs. non-interruptive reminders in outcomes of statin prescriptions.

Population and Design Considerations

Study Population:

Adult patients (age \geq 18 and < 75) who are treated by primary care providers at Vanderbilt University Medical Center and eligible for statin therapy but not currently on a statin are potentially eligible for this study. If a patient presents to a VUMC primary care clinic and meets the below inclusion and exclusion criteria, the patient will be enrolled to the study.

Inclusion Criteria

- 1. Patients age \geq 18 and < 75
- 2. Seen in primary care visit within Vanderbilt University Medical Center

PI: [name], MS

3. Eligible for statin therapy due to: 1) ASCVD 10-year risk \geq 10%, 2) Type 1 or 2 diabetes and age \geq 40, or 3) ASCVD diagnosis.

Exclusion Criteria

Patient records within the EMR indicate:

- 1. Already on statin, ezetimibe, bempedoic acid, or PCSK9 inhibitor
- 2. Last known LDL-C level < 100 mg/dL
- 3. Known to be pregnant or lactating
- 4. Palliative care
- 5. Statin allergy or adverse effect of statin
- 6. Rhabdomyolysis
- 7. Statin contraindicated due to liver disease, defined as 1) Decompensated liver disease, 2) AST or ALT >5 times the upper limit of normal, or 3) Total bilirubin > 1.5 mg/dL.
- 8. Statin contraindicated due to kidney disease, defined as 1) Dialysis or 2) Estimated glomerular filtration rate < 15 ml/min/1.73 m².
- 9. Has had coronary calcium computerized tomography
- 10. Less than 3 months since lipid panel resulted
- 11. Acute visit

Study Design

A pragmatic, single center, randomized, controlled, three-arm trial comparing the effect of interruptive alerts versus non-interruptive alerts versus no alerts recommending guideline-concordant statin prescription on statin prescription rates in primary care clinics.

Randomization and Patients' Enrollment

The study will have three arms: no reminder (routine care) arm, non-interruptive reminder arm, and interruptive reminder arm. A sequence of numbers of 0, 1, or 2, indicating one of the three arms will be randomly generated in a 1:1:1 ratio by a mechanism embedded in the EHR and assigned to patients presenting to a VUMC primary care clinic who are \geq 18 and < 75 years old. If the patient meets the above statin eligibility criteria and none of the exclusion criteria at the time of the visit, the patient is automatically enrolled in the study and randomized to the study arm assigned by the random number. The provider will receive either an interruptive reminder, a non-interruptive reminder, or no reminder, depending on the patient's assigned arm.

For repeat encounters, the provider will receive the same format of educational intervention (i.e., interruptive, non-interruptive, or no reminder) for a given patient throughout the course of the study. In the interruptive and non-interruptive alert arms, clinicians may or may not still be eligible for a repeat alert depending on how they interacted with the initial alert. If the patient is on a statin at the repeat visit, the clinician will not be shown a repeat alert. If the clinician did not prescribe a statin and chose an acknowledgement reason such as "statin is contraindicated", the alert will not be shown again. If the clinician simply closed or "canceled" the alert during the first visit, or if the clinician did not interact with a non-interruptive alert, the alert will be displayed again at the next visit; however, the patient will not be re-enrolled, and the primary endpoint measurement will not be re-taken relative to the firing of this BPA. Analysis will be

PI: [name], MS

performed on the unique patient level, rather than the visit level, where all eligible visits for an individual patient will be considered a single enrollment.

Sample Size Considerations

Based on baseline rates of eligible patient visits, we estimate a possible sample size of 3,931 over a course of 6 months, and 7,830 over a course of 12 months. If we assume that the statin prescribing rate for the control arm (i.e., no reminder, or routine care) is 3% (an estimate derived from current clinical data) and the statin prescribing rate for the interruptive statin reminder arm is 6% (an estimate based on a clinically meaningful doubling of the current prescribing rate with an active alert), a total of 3,006 patients (1,002 patients per arm) would provide 90% power to detect the difference in the statin prescribing rates between the two arms at a type I error rate of 0.05. With a conventional study design, our planned sample size could be a total of 3,000 patients (1,000 patients per arm).

However, considering that this study is a 3-arm trial with uncertainty on the effect size for both the interruptive statin reminder arm and the non-interruptive statin reminder arm, and potential chance of imbalance across arms, we designed an adaptive clinical trial with sample size adaptation. When the sample size reaches at least 2,250 patients (750 patients per arm), we will conduct an interim analysis to re-estimate the sample size. At the interim, we will calculate the conditional power and allow sample size re-estimation. Should the interim analysis confirm that the originally planned sample size of 3,000 patients (1,000 patients per arm) provides sufficient power, we will proceed without further sample size adjustment and stop recruiting patients when the sample size reaches 3,000 patients (1,000 patients per arm) or the stopping decision is made, whichever occurs later. However, if the interim analysis indicates the need for an increased sample size, we will adjust accordingly based on the re-estimated sample size with the constraint of the maximum sample size of a total of 6,000 patients (2,000 patients per arm).

Interventions

Interruptive reminder arm:

Providers will receive education via a pop-up alert at the time that the chart is opened for eligible patient visits assigned to the interruptive reminder arm.

Non-interruptive reminder arm:

Providers will be able to seek out education at their own initiative via an on-demand reminder within a section of the chart for eligible patient visits assigned to the non-interruptive reminder arm.

No reminder arm (routine care):

No alert recommending a statin will be displayed/available to the provider. The system will record eligibility through triggering a "silent" alert, which is not displayed to the clinician and exists solely for data collection purposes.

PI: [name], MS

[figure not shown]

Figure 1: Schematic procedure of arm assignment and enrollment.

Both the interruptive and the non-interruptive alerts will have the same format; only the manner in which it is displayed will differ. The reminder will alert clinicians that a statin is recommended for the patient and list the reasons the statin is indicated. It will give the clinicians a defaulted option for statin prescription as well as alternatives. If the clinician accepts the alert, an order for a statin will be placed in their "shopping cart" for convenience, and the order can be signed to prescribe the medication. If the clinician does not wish to prescribe a statin from the reminder, they can choose an acknowledgement reason.

Endpoints

Primary Endpoint

The primary outcome will be a binary outcome of statin prescription placed within 24 hours after enrollment BPA firing (interruptive, non-interruptive, or no reminder) (Yes/No).

Secondary Endpoints

This trial has two secondary outcomes:

- 1. A binary outcome of statin prescription placed within 12 months after enrollment BPA firing (Yes/No)
- 2. The patient's first LDL-C level measured during the follow-up between 30 days and 12 months since the enrollment visit.

PI: [name], MS

Exploratory Endpoints

- 1. A binary outcome of any non-statin lipid lowering agent prescription placed within 12 months after enrollment BPA firing (ezetimibe, PCSK9 inhibitor, or bempedoic acid) (Yes/No)
- 2. A binary outcome of any statin prescription filled within 12 months of enrollment BPA firing (Yes/No)
- 3. A binary outcome of new ASCVD event within 12 months of enrollment BPA firing (Yes/No)
- 4. Time from enrollment BPA firing to statin prescription

Statistical Approach

Target Population

The target population of the estimand will be the principal stratum that includes all participants meeting the above inclusion/exclusion criteria, for whom the randomization allocated by the EHR embedded tool is executed.

Analysis Dataset

- The analysis set will include all participants in the target population for the analysis of statin prescription placed within 24 hours (the primary endpoint), statin prescription placed within 12 months after enrollment BPA (a secondary endpoint), non-statin lipid lowering agent prescription placed within 12 months after enrollment (an exploratory endpoint), and new ASCVD event within 12 months of enrollment (an exploratory endpoint).
- For the analysis of the first LDL-C level measured during the follow-up (a secondary endpoint), statin prescription filling within 12 months of enrollment (an exploratory endpoint), and time from enrollment to statin prescription (an exploratory endpoint), the analysis set will include participants in the target population who do have the outcome measures but exclude patients whose outcomes are missing even after imputing the outcomes as described in the section, 'Handling Missing Data.'

Descriptive Analysis

General approach:

Categorical variables will be summarized using frequencies and proportions, and continuous variables will be described using means and standard deviations, as well as medians and interquartile ranges. The data also will be described graphically as needed. Missingness will be reported for each variable. No statistical comparisons between arms will be performed for these descriptive analyses.

Characteristics of the study sample:

Patient baseline demographic and clinical data as well as the provider information will be summarized overall and by intervention arm. The following variables will be described at time of enrollment:

• Patient sex (male, female, unknown)

PI: [name], MS

- Patient race (African American, Asian/Pacific Islander, Caucasian, Multiple, Native American, Other, Unknown)
- Patient self-reported ethnicity (Hispanic, Non-Hispanic, Unknown)
- Patient age (years)
- Patient comorbidities:
 - o Diabetes (Yes/No)
 - o ASCVD diagnosis (Yes/No)
 - o Congestive heart failure (Yes/No)
 - Hypertension (Yes/No)
 - o Peripheral artery disease (Yes/No)
 - o Stroke (Yes/No)
- Patient body mass index (BMI, kg/m²)
- Patient Charlson comorbidity index
- Type of patient statin therapy recommended to provider (moderate intensity, high intensity, high intensity and potential work up for LDL >= 190, low-dose statin for liver disease)
- Provider role (e.g., physician, physician assistant, resident physician, nurse practitioner)
- Prior statin prescription
- Visit type (in person or telemedicine)

Description of the endpoints:

All the endpoints will be summarized overall and by intervention arm.

Primary Analysis

General approach:

All primary analyses will be performed without covariate adjustment as the study interest lies in estimating the overall intervention effects observed in a diverse patient population in their usual clinical settings. To account for potential imbalance in covariate distribution across arms, secondary analyses will be performed with *a priori* selected covariate adjustment. All analysis results will be reported with point estimates and 95% confidence intervals (CIs). No adjustments for multiplicity will be made.

Analysis of the primary endpoint:

Statin prescription within 24 hours of enrollment BPA firing will be compared between intervention arms using a logistic regression with indicator variables for intervention arms.

Analysis of secondary endpoints:

Statin prescription placed within 12 months after enrollment BPA firing will be analyzed using a logistic regression. For the first LDL-C level measured during the follow-up, a linear regression analysis will be performed with intervention arm indicator variables. If the distribution of LDL-C levels is highly skewed, an ordinal logistic regression analysis will be used in place of a linear regression.

Analysis of the exploratory endpoints:

A logistic regression will be performed to compare the binary outcomes between intervention arms. Time from enrollment BPA firing to statin prescription will be compared between

PI: [name], MS

intervention arms using a Cox proportional hazard model and the differences in the outcome between arms will be visualized using Kaplan-Meier curve.

Secondary Analysis

The covariate adjusted analysis will be performed for the primary and the secondary outcomes using the same regression analysis methods with adjustment of the following covariates.

Covariates for the analysis of statin prescription (the primary endpoint and a secondary endpoint):

Patient age, sex, Charlson Comorbidity Index, type of patient statin therapy recommended to provider, baseline LDL-C level, ASCVD disease, diabetes, chronic kidney disease, prior statin prescription, visit type (in person or telemedicine), and provider role.

Covariates for the analysis of the first LDL-C level measured during the follow-up:

Patient age, sex, Charlson Comorbidity Index, type of patient statin therapy recommended to provider, baseline LDL-C level, ASCVD disease, diabetes, chronic kidney disease, prior statin prescription, visit type (in person or telemedicine), provider role, and time from enrollment to follow-up LDL-C level measurement.

Population-Level Summaries

Odds ratios (ORs) will be used for the analysis of binary (and ordinal) outcomes. For the analysis of the first LDL-C level measured during the follow-up, the estimates of mean differences in LDL-C levels, comparing interruptive reminder vs. no reminder arms, non-interruptive reminder vs. no reminder arms, and interruptive reminder vs. non-interruptive reminder arms will be used if a linear regress model is used. Hazard ratio (HR) will be used for the analysis of time to statin prescription.

Handling Missing Data

We do not expect missingness in our primary outcome and a secondary outcome of statin prescription within 12 months after BPA firing. Some missingness is expected for the first LDL-C level measured during the follow-up. For these missing outcomes, if a prior LDL-C level is available, the outcome will be imputed using the last known LDL-C level prior to the follow-up period; otherwise, the patient will be excluded in this analysis. For the exploratory outcomes, a complete case analysis will be performed without imputing the missing outcomes.

Missing covariates are not expected, or to be small percentage if occurs, which will be imputed using a single imputation. If missing data are substantial, multiple imputation will be used to handle missing covariates.

Intercurrent Events

To handle intercurrent event due to death or switching providers to other institutions, a whilealive strategy will be used.

Differential Treatment Effects

We will explore differential treatment effects for the primary endpoint only. Differential treatment effects will be explored by examining the interaction between the intervention arm

PI: [name], MS

indicators and each variable that could potentially interact with the interventions. The variables we consider include comorbidities (diabetes, ASCVD diagnosis) at time of enrollment, type of patient statin therapy recommended to provider (moderate intensity statin, high intensity statin, high intensity and potential work up for LDL >= 190, low-dose statin for liver disease), and provider role (e.g., physician, physician assistant, resident physician, nurse practitioner). Subgroup analyses will not be performed unless the analysis is suggestive of potential interaction.
